7.2.2. Interim analysis for PFS in patients unselected for PD-L1 expression

Throughout this section, references to PFS pertain to PFS by BICR assessment in patients unselected for PD-L1 expression.

The interim analysis for PFS for patients unselected for PD-L1 expression will be performed if H_{01} is rejected. No futility analysis will be performed for PFS in patients unselected for PD-L1 expression.

Let $u(t_1)$ and $u(t_F)$ denote the upper critical boundaries based on the test statistics Z_1 and Z_F for efficacy at the interim and the final analysis, respectively.

The critical values $u(t_1)$ for the interim analysis of PFS are determined such as

$$P_0(Z_1 \geq u(t_1)) = \alpha(t_1),$$

where P_0 denote the probabilities under the null hypothesis, and where $\alpha(t_1)$ denote the α spent, based on the predefined spending functions at information fraction t_1 (t_1 is calculated as the ratio of the number of PFS events observed at the time of the cut-off for the interim analysis and the total number of PFS events targeted for the final analysis).

The boundary for the final efficacy analysis will be calculated such that

$$\alpha(t_1) + P_0(Z_1 < u(t_1), Z_F \geq u_F) = 0.004$$

As described in Section 5.1.2, if the number of PFS events in the final analysis deviates from the target number of PFS events, the final analysis criteria will be determined as above taking into account the actual alpha spent at the interim analysis and the actual correlation between the two test statistics Z_1 and Z_F , so that the overall 1-sided significance level across all analyses and comparisons is preserved at 0.004.

7.2.3. Interim analysis for OS in PD-L1 positive patients

Throughout this section, references to OS pertain to OS in PD-L1 positive patients.

Let $u(t_i)$ and $u(t_F)$ denote the upper critical boundaries based on the test statistics Z_i and Z_F for efficacy at the i^{th} interim and the final analysis, respectively, and let $l(t_i)$ and $l(t_F)$ denote the lower critical boundary for futility at the i^{th} interim and final analysis, respectively, where $i=1, 2, 3$. For the final analysis, $l(t_F)=u(t_F)$.

In what follows P_0 and P_a denote the probabilities under the null hypothesis and the alternative hypothesis respectively, and $\alpha(t_i)$ and $\beta(t_i)$ denotes respectively the α and β spent based on the predefined spending functions at information fraction t_i (t_i is calculated as the ratio of the number of OS events observed at the time of the cut-off for the i^{th} interim analysis and the total number of OS events targeted for the final analysis).

The critical values $u(t_1)$ and $l(t_1)$ for the 1st interim analysis of OS are determined such as

$$P_0(Z_1 \geq u(t_1)) = \alpha(t_1) \text{ and } P_a(Z_1 \leq l(t_1)) = \beta(t_1) ,$$

Critical boundaries for the additional interim analyses and the final analysis of OS are calculated recursively as follows

$$u(t_2) \text{ is derived such that } \alpha(t_1) + P_0(Z_1 < u(t_1), Z_2 \geq u(t_2)) = \alpha(t_2) ,$$

$$l(t_2) \text{ is derived such that } \beta(t_1) + P_a(Z_1 > l(t_1), Z_2 \leq l(t_2)) = \beta(t_2) ,$$

$$u(t_3) \text{ is derived such that } \alpha(t_2) + P_0(Z_1 < u(t_1), Z_2 < u(t_2), Z_3 \geq u(t_3)) = \alpha(t_3) ,$$

$$l(t_3) \text{ is derived such that } \beta(t_2) + P_a(Z_1 > l(t_1), Z_2 > l(t_2), Z_3 \leq l(t_3)) = \beta(t_3)$$

The boundary for the final efficacy analysis is derived such that

$$\alpha(t_3) + P_0(Z_1 < u(t_1), Z_2 < u(t_2), Z_3 < u(t_3), Z_F \geq u_F) = \alpha'$$

where $\alpha' = 0.021$ for the analysis of OS in PD-L1 positive patients.

As described in Section 5.1.2, if the number of OS events in the final analysis deviates from the target number of OS events, the final analysis criteria will be determined as above taking into account the actual alpha spent at the interim analyses and the actual correlation between the three test statistics Z_i ($i=1, 2, 3$) and Z_F , so that the overall 1-sided significance level across all analyses and comparisons is preserved at 0.021.

7.2.4. Interim analysis for OS in patients unselected for PD-L1 expression

Throughout this section, references to OS pertain to OS in patients unselected for PD-L1 expression.

The interim analysis for OS for patients unselected for PD-L1 expression will be performed according to the testing strategy described in Section 7.1 and in Section 5.1.1. No futility analysis will be performed for OS for patients unselected for PD-L1 expression.

Let $u(t_i)$ and $u(t_F)$ denote the upper critical boundaries based on the test statistics Z_i and Z_F for efficacy at the i^{th} interim and the final analysis, respectively, where $i=1, 2, 3$.

In what follows P_0 denote the probability under the null hypothesis and $\alpha(t_i)$ denote the α spent based on the predefined spending functions at information fraction t_i (t_i is calculated as the ratio of the number of OS events observed at the time of the cut-off for the i^{th} interim analysis and the total number of OS events targeted for the final analysis).

The critical value $u(t_1)$ for the 1st interim analysis of OS are determined such as

$$P_0(Z_1 \geq u(t_1)) = \alpha(t_1) ,$$

Critical boundaries for the additional interim analyses and the final analysis of OS are calculated recursively as follows

$$u(t_2) \text{ is derived such that } \alpha(t_1) + P_0(Z_1 < u(t_1), Z_2 \geq u(t_2)) = \alpha(t_2) ,$$

$$u(t_3) \text{ is derived such that } \alpha(t_2) + P_0(Z_1 < u(t_1), Z_2 < u(t_2), Z_3 \geq u(t_3)) = \alpha(t_3)$$

The boundary for the final efficacy analysis is derived such that

$$\alpha(t_3) + P_0(Z_1 < u(t_1), Z_2 < u(t_2), Z_3 < u(t_3), Z_F \geq u_F) = \alpha'$$

where $\alpha' = 0.025$ or 0.021 or 0.004 for the analysis of OS in patients unselected for PD-L1 expression as determined according to the testing strategy described in Section 5.1.1.

9. APPENDICES

Appendix 1. Immune-Related Adverse Events

The MedDRA PTs and clusters for irAEs are defined in the Safety Review Plan (SRP) for avelumab.

Immune-related AEs (irAEs) will be programmatically identified as outlined in Table 18. This case definition is hierarchical, i.e., each step is only checked for patients and events that have already met the prior step.

Table 18. Case Definition for irAEs

Step	Selection Criteria	Additional Notes
1	Event selected based on a list of pre-specified MedDRA PTs within clusters. These are included in the SRP as Tier1 events (Immune-mediated xxxx). If AE matches the list then it is in for the next step	
2	AE onset during 1 st study drug administration or anytime thereafter through 90 days after last dose of study treatment.	This is regardless of start of new anti-cancer drug therapy and regardless of TEAE classifications
3	Answer in the AE eCRF page to ‘Was another treatment given because of the occurrence of the event’ is ‘YES’	
4	AE treated with corticosteroids or other immunosuppressant therapy. For endocrinopathies only: AE required hormone replacement	Look in the conmed pages for AE identifiers that match the AEs from Step 3. For each of such AEs if A) OR B) OR C) below are met then the AE is in for the next step A) conmed ATC code is in (H02A, H02B, D07, A01AC, S01BA, S01BB, L04AA, L04AB, L04AC, L04AD, L04AX, A07EA) and AE PT is in any of the irAE clusters. B) conmed ATC code is in (H03A, H03B) and AE PT is in one of the irAE clusters associated with “Immune-mediated endocrinopathies” C) conmed ATC code is A10A and AE PT is in the irAE cluster associated with “Immune-mediated endocrinopathies: Type I Diabetes Mellitus”


5
	
A) No clear etiology (other than immune mediated etiology)
 
B) Histopathology / biopsy consistent with immune-mediated event
 
Event is in if [Answer to 5B1 and 5B2 is YES (regardless of answer to 5A)] OR [Answer to 5B1 is YES AND answer to 5B2 is NO AND answer to 5A is NO] OR [Answer to 5B1 is NO AND answer to 5A is NO]
	
A) From the AE eCRF page Is the AE clearly related to an etiology other than immune-mediated etiology? Yes / No If answer is Yes, check all that apply:
 
 • Underlying malignancy / progressive disease. • Other medical conditions. • Prior or concomitant medications / procedures. • Other. Specify. 
B) From the AE eCRF page B1) Was there a pathology /histology evaluation performed to investigate the AE? Y/N B2) If answer to the above is Yes, does the pathology/histology evaluation confirms an immune mediated mechanism for the AE? Y/N B3) If pathology / histology evaluation performed to investigate the AE, provide summary of relevant findings of the pathology /histology report. (Free Text)

----------	---	--

The data set associated with irAEs may be refined based on medical review. The final data set including any changes based on medical review (e.g., addition of cases that are not selected by the programmatic algorithm) will be the basis of the irAE analyses.

Appendix 2. Infusion Related Reactions

For defining an AE as IRR the onset of the event in relation to the infusion of study drug and time to resolution of the event will be considered.

- All AEs identified by the MedDRA PT query describing signs and symptoms will be considered potential IRRs when onset is on the day of avelumab infusion (during or after infusion) and the event resolved with end date within 2 days after onset.
- All AEs identified by the MedDRA PTs of Infusion related reaction, Drug hypersensitivity, Anaphylactic reaction, Hypersensitivity, Type 1 hypersensitivity, will be considered potential IRRs when onset is on the day of avelumab infusion (during or after the infusion) or the day after the avelumab infusion (irrespective of resolution date).

The list of MedDRA PTs for ‘IRRs SIGNS and SYMPTOMS’ and PTs ‘IRRs CORE’ are defined in the SRP for avelumab.

Infusion-related reactions (IRRs) will be programmatically identified as outlined in Table 19 and will be identified for IV drugs only.

Table 19. Case Definition for IRRs – IV Study Drugs Administered Alone Or In Combination With Non-IV Study Drugs

Condition	Selection criterion
If AE meets [1 AND 2] OR [3 AND (4A OR 4B)] then AE is classified as an IRR	
1	PT is included in the ‘IRRs SIGNS and SYMPTOMS’ list
2	
 • AE onset date = date of infusion of study drug AND • AE timing related to study drug (‘DURING’, ‘AFTER’) AND • AE outcome in (‘RECOVERED/RESOLVED’, ‘RECOVERED/RESOLVED WITH SEQUELAE’, ‘RECOVERING/RESOLVING’) AND • AE end date – AE onset date <=2
3	PT is included in the ‘IRRs CORE’ list
4A	
 • AE onset date = date of infusion of study drug AND • AE timing related to study drug in (‘DURING’, ‘AFTER’)
4B	AE onset on the day after infusion

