**Table 5. Treatment Modification for Symptoms of Infusion-Related Reactions Caused by Avelumab**

NCI CTCAE Grade	Treatment Modification for Avelumab
Grade 1 – mild Mild transient reaction; infusion interruption not indicated; intervention not indicated.	Decrease the avelumab infusion rate by 50% and monitor closely for any worsening.
Grade 2 – moderate Therapy or infusion interruption indicated but responds promptly to symptomatic treatment (eg, antihistamines, NSAIDs, narcotics, IV fluids); prophylactic medications indicated for ≤24 hours.	Temporarily discontinue avelumab infusion. Resume infusion at 50% of previous rate once infusion-related reaction has resolved or decreased to at least Grade 1 in severity, and monitor closely for any worsening.
Grade 3 or Grade 4 – severe or life-threatening Grade 3: Prolonged (eg, not rapidly responsive to symptomatic medication and/or brief interruption of infusion); recurrence of symptoms following initial improvement; hospitalization indicated for clinical sequelae. Grade 4: Life-threatening consequences; urgent intervention indicated.	Stop the avelumab infusion immediately and disconnect infusion tubing from the patient. Patients have to be withdrawn immediately from avelumab treatment and must not receive any further avelumab treatment.
IV=intravenous, NCI CTCAE=National Cancer Institute Common Terminology Criteria for Adverse Events, NSAIDs=nonsteroidal anti-inflammatory drugs.	

Once the avelumab infusion rate has been decreased by 50% due to an infusion-related reaction, it must remain so for all subsequent infusions.

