6.6.4. Other significant adverse events

The frequency (number and percentage) of patients with each of the following will be presented for irAEs, by treatment arm:

- irAEs leading to death, by Cluster and PT
- irAEs, by Cluster and PT
- irAEs, Grade ≥ 3 , by Cluster and PT
- irAEs leading to discontinuation of avelumab, by Cluster and PT
- irAEs leading to discontinuation of axitinib, by Cluster and PT
- irAEs leading to discontinuation of sunitinib, by Cluster and PT
- irAEs leading to discontinuation of any study drug, by Cluster and PT
- irAEs leading to discontinuation of all study drugs, by Cluster and PT
- Serious irAEs, by Cluster and PT

The listing of all irAEs will also be provided with the relevant information with a flag for irAEs with onset outside of the on-treatment period.

The frequency (number and percentage) of patients with each of the following will be presented for IRRs, by treatment arm:

- IRRs leading to death, by PT
- IRRs, by PT
- IRRs, Grade ≥ 3 , by PT
- IRRs leading to discontinuation of avelumab, by PT
- Serious IRRs, by PT
- Time related to first onset of an IRR (infusion 1, infusion 2, infusion 3, infusion 4 or later)

The listing of all IRRs will also be provided with the relevant information with a flag for IRRs with onset outside of the on-treatment period.

In addition, the following analyses will be presented for Tier-1 (irAEs and IRRs as defined in Appendices 1 and 2) and Tier-2 events separately. P-values and CIs for risk difference will be calculated based on the unconditional exact method by Santner and Snell (1980). No additional analyses will be presented for Tier-3 AEs.

- Frequency (number and percentage) of patients with each of the following by treatment arm and PT or Clustered Term:

- Tier-2 AEs
- Tier-2 AEs Grade ≥ 3
- Point estimate for risk difference and 95% CI for risk difference (experimental arm vs comparator arm) for each of the following by PT or Clustered Term:
 - irAEs
 - irAEs Grade ≥ 3
 - Tier-2 AEs
 - Tier-2 AEs Grade ≥ 3
- 2-sided p-value associated with risk difference (experimental arm vs comparator arm) for each of the following by PT or Clustered Term:
 - irAEs
 - irAEs Grade ≥ 3
- The p-values and CIs reported are not adjusted for multiplicity and should be used for screening purposes only. The 95% CIs are provided to help gauge the precision of the estimates for the risk difference and should be used for estimation purposes only.

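### SAP Table 19 never labels a symptom-coded reaction as an IRR if it is fatal, unresolved or longer than 2 days, so the fatal IRR table excludes such events by construction and other severe-IRR tables may undercount

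*SAP*

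**What the plan says.** SAP Appendix 2 gives two routes to an IRR, joined in Table 19 by the rule "If AE meets [1 AND 2] OR [3 AND (4A OR 4B)] then AE is classified as an IRR".

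- **Symptom route (conditions 1 and 2).** The preferred term is on the signs-and-symptoms list. Onset is on the infusion day, during or after the infusion. The outcome is recovered, "RECOVERED/RESOLVED WITH SEQUELAE" or recovering, and "AE end date – AE onset date <=2". The text above the table puts the last part as "and the event resolved with end date within 2 days after onset".
- **CORE route (conditions 3 and 4).** The text names the terms as "Infusion related reaction, Drug hypersensitivity, Anaphylactic reaction, Hypersensitivity, Type 1 hypersensitivity". Onset may be on the infusion day or the day after, and the event counts "irrespective of resolution date". No outcome is required.

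Both term lists are held in the Safety Review Plan, which is not among the documents.

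SAP 6.6.4 then plans IRR tables that include "IRRs leading to death, by PT", and further tables for Grade 3 or higher, serious events and discontinuation of avelumab. SAP 6.6.1 treats an event as leading to death if its outcome is fatal or its grade is 5.

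SAP Appendix 1 lets medical review add immune-related events that its algorithm missed. Appendix 2 has no such provision for IRRs.

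**The concern.** Condition 2 selects on outcome and duration, and both are plausibly linked to severity. Protocol Table 5 describes a Grade 3 infusion reaction as "Prolonged (eg, not rapidly responsive to symptomatic medication and/or brief interruption of infusion); recurrence of symptoms following initial improvement", or one needing hospitalization for its sequelae. A reaction of that kind, entered as its component symptoms rather than under a diagnostic term, is more likely than a mild one to fail the 2-day test. If it is fatal it fails the outcome test outright.

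IRRs are an adverse event of special interest (SAP 3.5.1). A zero for symptom terms in the fatal IRR table would look like an observation when it is a consequence of the definition. The label is also used elsewhere: for IRR summaries by anti-drug-antibody status (SAP 6.2.6.3), and to decide which infusion-day events are left out of the analysis of events leading to interruption (SAP 6.6.1.3).

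**Working it through.** There is no figure in the plan to reproduce, so the check is to run the rule over the possible cases and compare the result with the tables it feeds.

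**Step 1. Apply the rule.** Timing is taken as during or after infusion for infusion-day onsets. Durations tried were 0, 1, 2, 3 and 10 days, and no end date.

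| Route | Onset | Outcome | End minus onset | IRR? |
|---|---|---|---|---|
| Symptom | Infusion day | Recovered, with sequelae, or recovering | 0, 1 or 2 days | Yes |
| Symptom | Infusion day | The same three | 3 days, 10 days, or no end date | No |
| Symptom | Infusion day | Fatal, not recovered, unknown | Any | No |
| Symptom | Day after | Any | Any | No |
| CORE | Infusion day or day after | Any | Any | Yes |

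Grade appears nowhere in the rule. A symptom-coded Grade 3 or 4 event that resolves in 2 days is therefore kept, and one that takes 3 days is dropped.

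**Step 2. Compare with the planned tables.** The fatal IRR table needs a fatal outcome or Grade 5. The symptom route needs a recovered or recovering outcome. The two can meet only if a Grade 5 event is recorded as recovered, which would be a data inconsistency. For the Grade 3 or higher, serious and discontinuation tables there is partial overlap: short events enter, long or unresolved ones do not.

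**Step 3. Check the end date.** The text requires the event to have resolved, whereas Table 19 also accepts RECOVERING/RESOLVING and still needs an end date. Under SAP 5.3.2.2 a completely missing stop date is not imputed, so the 2-day test cannot be met. A stop date that lacks only the day is set to the end of the month (or to the date of death, if month-end would fall after it), so even a one-day reaction can fail.

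**Step 4. Can the loss be sized?** The Phase 1b figures in Protocol 1.2.3 are 7 of 47 patients with an IRR and 1 of 47 with a Grade 3 IRR. With 1:1 randomization of about 830, Arm A has about 830 / 2 = 415 patients.

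- All IRRs: 415 × 7/47 = 61.8
- Grade 3 IRRs: 415 × 1/47 = 8.8

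Let s be the share of Grade 3 reactions coded only by symptoms, and d the share of those that are longer than 2 days, unresolved or fatal. Then the number lost is 8.8 × s × d. The documents give neither s nor d, so these values are assumptions:

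- s = 0: 0 lost
- s = 0.25, d = 0.5: 1.1 lost
- s = 0.5, d = 0.5: 2.2 lost
- s = 1, d = 1: 8.8 lost

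The range is the whole of 0 to about 9. The Phase 1b counts also seem to be reported under the term infusion-related reaction, which is a CORE term. On that reading Table 19 would keep every one of them, and they say nothing about symptom-coded events. The projection shows scale only and does not estimate the loss.

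**The case against.** The strongest case against has four parts.

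1. The CORE list holds the diagnostic terms a site would be expected to use for a serious reaction, and these are kept whatever their outcome or length. A reader might infer from condition 2 that the IRR definition removes severe reactions generally. It does not: CORE-coded reactions stay in, and so do symptom-coded events of Grade 3 or higher that resolve within 2 days. **This stands.**
2. Nothing leaves the safety report. Dropped events still appear among treatment-emergent events by worst grade and fatal events (SAP 6.6.1.1), events leading to discontinuation of avelumab (6.6.1.4), deaths (6.6.2) and serious events (6.6.3). IRRs are identified for intravenous drugs only, and the risk differences and p-values in 6.6.4 are listed for immune-related events and, without p-values, Tier-2 events. No between-arm IRR comparison is affected. **This stands**, but the general tables cannot show which severe or fatal events were infusion reactions, and that is what the IRR tables are for.
3. The time limit has a purpose. Fever, chills and headache are non-specific, and without a limit many unrelated events starting on an infusion day would become IRRs. **This stands for Grade 1 and 2 events.** It is a weaker reason for excluding a fatal or Grade 3 event.
4. Prolonged in Protocol Table 5 is defined by response to treatment or to interruption of the infusion, not in days, and recurrence or hospitalization need not mean more than 2 days. **This stands**: the link between Grade 3 and failing the 2-day test is a reasonable inference that the documents do not quantify.

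A reader might also infer a definite drop in the Grade 3 rate from the Phase 1b figures. Step 4 shows why that is not supported.

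**Conclusion.** The exclusion is certain from the SAP text. No symptom-coded reaction that is fatal, unresolved, longer than 2 days or without an end date can be classified as an IRR at any grade, and Appendix 2 states no review step to restore it. The fatal IRR table therefore cannot contain a symptom-coded event, apart from a Grade 5 event recorded as recovered.

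For the Grade 3 or higher, serious and discontinuation IRR tables the conclusion is weaker: they may undercount, by an amount that depends on coding practice and on a term list not in the documents. The undercount may be zero if severe reactions are coded to CORE terms. No efficacy conclusion depends on it. The change is still worth making, because the rule and the tables it feeds conflict and the correction is cheap.

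**What to change.** Amend SAP Appendix 2, Table 19, condition 2:

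- For signs-and-symptoms terms with onset during or after infusion on the infusion day, waive the outcome and duration criteria when the event is Grade 3 or higher, is fatal (fatal outcome or Grade 5), or has drug withdrawn as the action taken with avelumab.
- Keep the 2-day resolution rule, including the need for an end date, for all other Grade 1 and 2 symptom terms. Dropping the end-date test for every recovering event would let a long, mild symptom in and undo the rule.
- Reconcile the text, which requires resolution, with the table, which also accepts RECOVERING/RESOLVING.
- Report the IRR counts with and without the waiver.

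The cost is a few lines of wording and programming. Some unrelated severe events that begin on an infusion day may be counted as IRRs; how many cannot be judged without the term list, but the two-way count makes them visible. A serious Grade 1 or 2 symptom event that lasts more than 2 days and does not lead to withdrawal would still be left out of the serious IRR table.
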